4.5.1.1 Investigational Product Handling

The investigational product manager will select the MEDI4920 vials assigned by the IXRS to prepare the subject's dose. For subjects assigned to placebo, the sites should use prefilled IV saline bags only.

Do not remove MEDI4920 from 2°C to 8°C (36°F to 46°F) storage until all procedures for subject dosing have been completed. When preparing a dose for administration, immediately remove the vials from the carton and replace the carton in 2°C to 8°C (36°F to 46°F) storage.

The investigational product manager/unblinded study personnel must ensure that only the unblinded team members have access to the areas of the pharmacy where the investigational product is being prepared.

4.5.1.2 Investigational Product Inspection

Each vial selected for dose preparation should be inspected. MEDI4920 is supplied as a sterile lyophilized drug product with post-reconstitution concentration of 50 mg/mL.

If there are any defects noted with the investigational product, the investigator and site monitor should be notified immediately. Refer to the Product Complaint section for further instructions (Section 4.5.1.9).

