4.5 Investigational Products

4.5.1 Identity of Investigational Products

MedImmune will provide the investigator(s) with investigational product (Table 4.5.1-1) using designated distribution centers.

Investigational Product	Manufacturer	Concentration and Formulation as Supplied
MEDI4920 (250 mg/vial)	MedImmune, LLC	20 mL lyophilized vial with a nominal 250 mg of MEDI4920 at a post-reconstitution concentration of 50 mg/mL, containing 10 mM sodium monobasic/dibasic phosphate, 250 mM sucrose and 0.02% (w/v) polysorbate 80, pH 7.4
Placebo	Provided by the site	0.9% saline for injection

Table 4.5.1-1	Identification of Investigational Products
---------------	--

(w/v) = (weight/volume)

MEDI4920 will be supplied by MedImmune to the site in containers with identical appearances in coded, open-label kits. Each kit has a unique number that is printed on all labels within the kit (ie, the outer carton label and the label of each container within the carton). Each carton is labeled with a unique number range that corresponds to the labeled

number series of the containers within the carton. Placebo will be prefilled IV saline bags sourced by each site.

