4.5.1.9 Reporting Product Complaints

Any defects with the investigational product must be reported *immediately* to the MedImmune Product Complaint Department by the site with further notification to the site monitor. All defects will be communicated to MedImmune and investigated further with the Product Complaint Department. During the investigation of the product complaint, all investigational product must be stored at labeled conditions unless otherwise instructed.

MedImmune contact information for reporting product complaints:

Mail: MedImmune Attn: Product Complaint Department [name]

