4.6 Treatment Assignment and Blinding

4.6.1 Methods for Assigning Treatment Groups

An IXRS will be used for randomization to a treatment group and assignment of investigational product kit numbers if assigned to an active treatment arm. A subject is considered randomized into the study when the investigator notifies the IXRS that the subject

meets eligibility criteria and the IXRS provides the assignment of treatment group and allocates active treatment if assigned to the active treatment arm.

Subjects will be randomized in a 4:1 ratio (Cohort 1), in a 5:2 ratio (Cohort 2), in a 3:1 ratio (Cohort 3), and in a 5:2 ratio (Cohort 4) to receive either MEDI4920 or placebo respectively as described in Table 3.1.2-1.

Investigational product (MEDI4920 or placebo) must be administered the same day the investigational product is assigned. If there is a delay in the administration of investigational product such that it will not be administered within the specified timeframe, the study monitor must be notified immediately.

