4.6.2 Methods for Ensuring Blinding

This is a double-blind study in which MEDI4920 and the saline placebo are not identical in appearance. As such, neither the subject/legal representative nor any of the investigator or sponsor staff who are involved in the treatment or clinical evaluation of the subjects will be aware of the treatment received (ICH E9) (see Section 4.6.4 for unblinding related to interim analysis). For maintaining the blinding of the principal investigator, site staff, sponsor, Contract Research Organization (CRO) or staff, a local unblinded pharmacy staff member will be nominated by each site and will have the responsibility of allocating, dispensing and preparing the investigational product in order to maintain the study blind. In addition, a separate unblinded monitor will be used for the oversight of investigational product management. If treatment allocation for a subject becomes known to the investigator or other study staff involved in the management of study subjects, the sponsor must be notified *immediately*.

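### Protocol 4.5.1.2 sends vial-defect notices to the blinded investigator, although only MEDI4920 subjects have vials, so a notice traceable to a subject's dose reveals active treatment

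*Protocol*

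**What the plan says.** **Supply.** Protocol Section 4.5.1 describes MEDI4920 as lyophilized vials in coded, open-label kits. For the comparator, "Placebo will be prefilled IV saline bags sourced by each site". Section 4.5.1.1 adds: "For subjects assigned to placebo, the sites should use prefilled IV saline bags only".

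**Inspection and notice.** Section 4.5.1.2 states: "Each vial selected for dose preparation should be inspected". It continues that, for any defect found in the product, "the investigator and site monitor should be notified immediately". Section 4.5.1.9 has defects reported to the sponsor's Product Complaint Department "by the site with further notification to the site monitor".

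**Blinding.** Section 4.6.2 acknowledges that drug and saline differ in appearance. It requires that investigator and sponsor staff who treat or evaluate subjects do not know the treatment. A local unblinded pharmacy staff member allocates, dispenses and prepares product, and "a separate unblinded monitor will be used for the oversight of investigational product management". If allocation becomes known to the investigator, the sponsor must be told at once. SAP Section 2.3 repeats the pharmacy and monitor arrangements.

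**The concern.** The two products look different, so the blind rests on keeping pharmacy information away from the people who treat and assess subjects. Section 4.5.1.2 names the investigator as a recipient of information that arises in the pharmacy, during preparation, from an object that exists in one arm only. It sets no limit on what the notice may say. A site that follows 4.5.1.2 could therefore create the breach that 4.6.2 requires to be reported.

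The investigator assesses the severity of adverse events and their relationship to product (Section 5.4) and scores the physician global assessment (4.3.6.3), which enters the CDAI (4.3.6.4). Unblinding by this route can never fall on a placebo subject, and its chance rises with the number of vials per dose. Any resulting bias would thus be one-sided and graded by dose, in a study meant to describe a dose-response relationship.

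**Working it through.** The plan states no figure to reproduce. The main check is a comparison of the text; the arithmetic only gives the scale.

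**Step 1: does a vial identify the arm?** Yes. Sections 4.5.1 and 4.5.1.1 give vials to active subjects and saline bags to placebo subjects. Section 4.5.1.5 confirms that placebo bags need no further preparation.

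**Step 2: can a notice be tied to a subject?** Often. Inspection takes place when vials are selected for a particular dose, and Section 4.6.1 requires product to be given on the day it is assigned. Section 3.1.1 plans about 15 sites and cohorts of 10, 14, 16 and 14, so 10/15 = 0.7 to 16/15 = 1.1 subjects per site per cohort on average. A notice on a dosing day would often point to one person.

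**Step 3: what does the investigator learn?** The chance that a subject is on active drug, before any notice, follows from the planned numbers (Section 3.1.1):

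- Cohort 1: 8/10 = 80%
- Cohort 2: 10/14 = 71.4%
- Cohort 3: 12/16 = 75%
- Cohort 4: 10/14 = 71.4%

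After a vial-defect notice linked to that subject it is 100%.

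**Step 4: exposure by dose.** Vials per dose are 1, 2, 4 and 6 (Section 4.5.1.5), with 7 doses per subject (Section 3.1.1). Vials per subject = 7 × vials per dose. The total is 56 + 140 + 280 + 504 = 980 vials, all in the 40 active subjects and none in the 14 placebo subjects.

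**Step 5: scale under assumed defect rates.** The documents give no rate, so r is an assumption. The chance of at least one defect for a subject with n vials is 1 − (1 − r)^n. The expected count is that chance times the group size, summed over groups.

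| Dose | Active N | Vials per subject | r = 0.2% | r = 0.5% | r = 1% |
|---|---|---|---|---|---|
| 75 mg | 8 | 7 | 1.4% | 3.4% | 6.8% |
| 500 mg | 10 | 14 | 2.8% | 6.8% | 13.1% |
| 1000 mg | 10 | 28 | 5.5% | 13.1% | 24.5% |
| 1500 mg | 12 | 42 | 8.1% | 19.0% | 34.4% |
| Expected active subjects | 40 | | 1.9 | 4.5 | 8.4 |

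For example, at 1500 mg and r = 1%: 1 − 0.99^42 = 0.344, and 12 × 0.344 = 4.1 subjects. The counts assume full dosing, independent defects, and that every notice is traceable and reveals treatment. They are therefore ceilings on the expected number at each assumed rate.

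**The case against.** **A notice need not unblind.** Table 4.5.1-1 and Section 4.6.1 count placebo as investigational product, so a faulty saline bag could also lead to a notice, and 4.5.1.2 does not require the notice to name a subject or a vial. This stands as a limit: only a notice that mentions a vial, or can be linked to a subject's vials, reveals treatment. It does not remove the problem, because the only inspection that 4.5.1.2 describes is of vials and nothing restricts the content of the notice.

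**The site monitor may be the unblinded one.** Section 4.6.2 provides a separate unblinded monitor for product oversight, and a vial defect falls within that task. This stands: the recipient named in 4.5.1.2 and 4.5.1.9 is ambiguous, and the conflict lies with the investigator.

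**The consequences are contained.** The primary endpoint is incidence of events, with severity and causality as breakdowns. Joint counts are made by an independent blinded assessor (4.3.6.1). Changes to background methotrexate up to Week 12 are limited to safety or tolerability (4.5.2.1). All of this is fair and limits the damage. It does not cover the severity and causality judgments or the physician global assessment. Section 5.1 also leaves it partly to the investigator whether an abnormal laboratory finding counts as an adverse event.

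**A stronger reading concerns the IXRS.** Section 4.6.1 has the investigator notify the system, after which "the IXRS provides the assignment of treatment group and allocates active treatment if assigned to the active treatment arm". A reader might infer that the investigator sees the allocation and that all 54 subjects are unblinded at randomization. The text does not support this, because it names no recipient. Section 4.5.1.1 has the product manager select the vials that the IXRS assigns, Section 4.5.6 calls that manager unblinded, and Section 4.6.2 places allocation with unblinded pharmacy staff. The emergency unblinding procedure in 4.6.3.1 would have no purpose if the investigator already knew.

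**Conclusion.** The conflict between 4.5.1.2 and 4.6.2 is real but narrow. As written, a vial-defect notice goes to an investigator who must stay blinded, and it reveals active treatment whenever it can be linked to a subject's dose. No other section limits its routing or content.

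The direction is certain: only active subjects can be affected, and the chance rises with dose. The size is unknown. The ceiling of about 2 to 8 of 40 active subjects depends on assumed defect rates of 0.2% to 1% and on the simplifications stated with the table. The conflict itself depends on none of these. The documents do not show that the IXRS discloses treatment to the investigator or that the blinded monitor is the one notified. The point merits a correction because the blind depends on separating staff and the repair is small.

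**What to change.** - **Sections 4.5.1.2 and 4.5.1.9:** have the unblinded investigational product manager report vial defects only to the unblinded monitor and the Product Complaint Department. Remove the investigator as a recipient, and say unblinded where the monitor is named.
- **Dosing delays:** if the investigator must know that a dose is held up, send a content-neutral notice that mentions neither vials nor kits and would read the same in either arm.
- **Section 4.6.1 (optional clarification):** state that IXRS treatment and kit output goes only to unblinded pharmacy staff and that the investigator receives a blinded confirmation of randomization.

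The cost is a few sentences of protocol text and, for the optional item, a check of IXRS user roles. The unblinded manager, pharmacy staff member and monitor already exist under 4.5.6 and 4.6.2, so no staff, visits or analyses are added.

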4.5.1.3 Dose Preparation Steps

No incompatibilities between MEDI4920 and plastics passing compatibility tests (ie, polyethylene bags; polyethylene and polyvinyl chloride infusion lines; polypropylene and polycarbonate syringes for IV infusion using IV infusion pump) have been observed. MEDI4920 does not contain preservatives and any unused portions must be discarded. Preparation of investigational product and IV bags is to be performed aseptically. Total in-use storage time from reconstitution of investigational product/needle puncture of the investigational product vial to start of administration should not exceed 4 hours at room temperature or 24 hours at 2°C to 8°C (36°F to 46°F). If storage time exceeds these limits, a new dose must be prepared from new vials.

Each vial of investigational product must be reconstituted with 5.0 mL of sterile water for injection to achieve 5.5 mL (5 mL nominal) of 50 mg/mL MEDI4920.

4.5.1.4 Reconstitution Procedure

Slowly add 5.0 mL of sterile water for injection by tilting the vial to one side such that the liquid stream is directed along the vial wall and not directly onto the lyophilized cake. Gently swirl the solution and repeat this procedure until all solids are dissolved. DO NOT SHAKE OR VIGOROUSLY AGITATE THE VIAL. Visually inspect the solution to ensure that the entire content of the lyophilized cake is completely reconstituted. The reconstituted solution should appear clear to opalescent. A thin layer of bubbles on the surface of the liquid is normal.

4.5.1.5 Preparation of Intravenous Dose

For Subjects Randomized to the MEDI4920 Group:

Preparation of MEDI4920 doses for IV infusion with an IV infusion pump:

The dose preparation steps are as follows:

- 1. For each of the IV doses (ie, 75, 500, 1000, and 1500 mg), the volume of 0.9% saline (weight/volume [w/v]) equivalent to volume of MEDI4920 is removed first and then the required volume of MEDI4920 will be added to a prefilled IV bag (Table 4.5.1.5-1). Syringes used to prepare the IV bag must be polycarbonate or polypropylene.
- A vial should be used only one time to prepare a single dose. The required volume of MEDI4920 (Table 4.5.1.5-1) will be obtained by pooling the contents of as many MEDI4920 vials as necessary (ie, 1 vial for the 75 mg dose, 2 vials for the 500 mg dose, 4 vials for the 1000 mg dose, and 6 vials for the 1500 mg dose) with an appropriately sized syringe. For ease of preparation, a 1.5-inch 20-gauge withdrawal needle should be used. Use a new needle for withdrawing investigational product from each vial.
- 3. Gently mix the contents of the IV bag. The admixture should then be inspected to ensure the solution is clear.

Table 4.5.1.5-1MEDI4920 Dose Preparation for IV Infusion with an IV
Infusion Pump

Dose (mg)	Prefilled IV Bag Size (mL)	Volume of Saline Removed from IV Bag (mL)	MEDI4920 Dose Volume Added to IV Bag (mL)
75	50	1.5	1.5
500	100	10	10
1000	250	20	20
1500	250	30	30

IV = intravenous; FTIH = first time in human; SAD = single ascending dose.

Note: The maximum concentration of reconstituted investigational product solution will not exceed that used in the FTIH SAD study.

For Subjects Randomized to the Placebo Group:

Preparation of placebo for IV infusion with an IV infusion pump:

For each of the doses, the prefilled IV saline bag size to be used is listed in Table 4.5.1.5-2. No additional IV bag preparation is required.

Table 4.5.1.5-2Placebo Dose Preparation for IV Infusion with an IV
Infusion Pump

Dose (mg)	Prefilled IV Bag Size (mL)
75	50
500	100
1000	250
1500	250

IV = intravenous

During preparation of the investigational product infusion, the capacity of the tubing should be calculated in order to adjust the volume of investigational product solution needed to prime the IV tubing. This step is necessary because the same volume of saline will be needed at completion of the infusion to flush the IV tubing in order to deliver the complete volume of investigational product solution. Because the IV tubing contains investigational product solution, the flush must be infused using the same infusion rate as that used for the investigational product solution in the infusion bag.

For example, if the IV tubing capacity is 15 mL, the IV tubing should be primed with 15 mL of investigational product solution from the infusion bag before initiating the infusion. Once the infusion bag is empty, the IV tubing should be flushed with at least 15 mL of 0.9% saline (w/v) via the infusion pump at the same rate as dosing.

The start time of the infusion will be the time when infusion of the investigational product solution from the infusion bag (with IV tubing primed with investigational product solution) is started. The stop time of the infusion will be the time when the IV tubing has been flushed with a volume of 0.9% normal saline equivalent to IV tubing capacity (eg, 15 mL for the example above) to administer the residual investigational product solution.

4.5.1.6 Intravenous Administration

All Cohorts (1-4) will be administered investigational product via IV infusion using an IV infusion pump.

Each subject in each cohort must receive the entire volume of investigational product solution in the IV bag. Table 4.5.1.6-1 provides the duration of infusion and flow rate by dose level. Investigational product must be infused through a low-protein binding 0.2- or 0.22-µm in-line filter using an IV infusion pump.

 Table 4.5.1.6-1
 Intravenous Administration of Investigational Product

Cohort	Dose (mg)	Total Volume in IV Bag (mL)	Minimum Administration Time (min)	Flow Rate at Minimum Time (mL/min)
1	75	50 (IV bag)	30	1.7 mL/min
2	500	100 (IV bag)	60	1.7 mL/min
3	1500	250 (IV bag)	90	2.8 mL/min
4	1000	250 (IV bag)	90	2.8 mL/min

IV = intravenous; min = minute; TBD = to be determined

4.5.1.7 Treatment Administration

The first day of dosing is considered Day 1.

Each dose of investigational product should be administered using the following guidelines:

- Female subjects must have a negative urine pregnancy test prior to receiving MEDI4920 or placebo.
- A physician must be present at the site or immediately available to respond to emergencies during administration of investigational product. Fully functional resuscitation facilities should be available.
- Investigational product will be administered as a single IV infusion as described in Table 4.5.1.6-1.

4.5.1.8 Monitoring of Dose Administration

Vital signs (BP, heart [pulse] rate, respiratory rate, and body temperature) will be obtained as outlined in Table 4.2.1-1, Table 4.2.2-1, and Table 4.2.3-1). In addition, if signs and symptoms indicative of an infusion reaction occur, the infusion will be stopped or slowed according to the judgment of the investigator.

As with any biologic product, allergic reactions to dose administration are possible. Therefore, appropriate drugs and medical equipment to treat acute anaphylactic reactions must be immediately available, and study personnel must be trained to recognize and treat anaphylaxis.

4.5.1.9 Reporting Product Complaints

Any defects with the investigational product must be reported *immediately* to the MedImmune Product Complaint Department by the site with further notification to the site monitor. All defects will be communicated to MedImmune and investigated further with the Product Complaint Department. During the investigation of the product complaint, all investigational product must be stored at labeled conditions unless otherwise instructed.

MedImmune contact information for reporting product complaints:

Mail: MedImmune Attn: Product Complaint Department [name]

4.5.2 Additional Study Medications

4.5.2.1 Background Medications for RA

All permitted background medications from initiation of screening through to the end of the study must be recorded in the source records and include the specific indication for use as well as the dose, start and stop dates, frequency, and route of administration.

MTX and Other cDMARDs

All subjects (except patients with intolerance to MTX or having been switched to another cDMARD after MTX failure) must be on MTX (7.5 to 25 mg/week) administered the same route (oral or injectable), for at least 12 weeks and at a stable dose for at least 6 weeks prior to screening. Subjects must continue with the same dose and route of administration for MTX during the 12-week treatment period (Days 1 to 85). Any dose changes in background MTX should be discussed and agreed with the medical monitor. Changes in MTX dose are permitted for safety/tolerability reasons (which must be clearly documented) or, after Week 12 for control of disease activity.

To minimize MTX toxicity, it is recommended that subjects receive 5.0 mg/week folic acid during the study as a single or divided dose.

It is recommended that MTX is withheld if liver function tests (LFTs), particularly ALT or AST enzymes, are increased to > $3 \times$ ULN and MTX dose should be reduced by 2.5 mg/week if LFT enzymes are increased between 2 and $3 \times$ ULN. After normalization of the LFT, MTX can be reinitiated and/or titrated up to the dose used prior to modulation. In case of newly occurred blood cytopenias (WBC < 3×10^9 /L, neutrophil count < 2×10^9 /L, platelet count < 150×10^9 /L) MTX should be withheld until blood cell counts recover.

Protocol-permitted alternative cDMARDs (for subjects with documented MTX intolerance or if subjects have been treated with this DMARD after a previous MTX failure) are leflunomide, sulfasalazine, hydroxychloroquine, azathioprine, D-penicillamine, and cyclosporine. These must be given at the doses specified by the local RA treatment guidelines and the local Summary of Product Characteristics. Subjects should be treated with the alternative cDMARD for at least 12 weeks and at a stable dose for at least 6 weeks prior to screening. Subjects must continue with the same dose and route of administration during the 12-week treatment period (Days 1 to 85). Changes in dose are permitted for safety/tolerability reasons (which must be clearly documented) or, after Week 12 for control of disease activity.

Corticosteroids

Corticosteroids should be maintained at a stable oral dose (< 10 mg equivalent prednisone/day) for the duration of the study through to the end of the 12-week treatment period unless changes are needed for safety reasons. Any change in background oral corticosteroids, or addition of injectable corticosteroids, is prohibited from 4 weeks prior to Day 1 up to Week 12 (Day 85), unless used for the treatment of a non-RA AE. It is strongly recommended to avoid changes in corticosteroids dosage within 4 weeks prior to the Week 12 (Day 85) visit to avoid confounding the evaluation of efficacy. After Week 12, a change in oral corticosteroid dose and/or addition of injectable corticosteroids for control of disease activity is permitted. A maximum of 2 intra-articular injections of corticosteroids (up to 40 mg of triamcinolone or equivalent) can be allowed as required to control severe/refractory mono/oligoarthritis during the treatment period (no more than 4 joints allowed to be treated). Treated joint(s) will need to be excluded from the joint counts until 12 weeks post-injection. Intra-articular steroid injections are not allowed within 4 weeks prior to the Day 85(Week 12) visit to avoid confounding the evaluation of efficacy. Inhaled

or topical corticosteroids given for asthma, COPD, or dermatological conditions are allowed provided doses are stable between screening and Day 85 visit.

Analgesics/NSAIDs

Analgesics and NSAIDs given primarily for RA signs and symptoms should be maintained at a stable dose for the duration of the study through to the end of the 12-week treatment period (Day 85) unless changes are needed for safety/tolerability reasons or inadequate response after the Week 12 visit. Subjects should refrain from taking the usual morning dose of analgesics on visit days until after all clinical assessments have been completed.

